### 3.1.2 Treatment Groups for Data Summaries

Unless otherwise specified, analyses using the ITT analysis set will be restricted to the MTX Run-in Period and will be presented as one treatment group called "MTX".

The mITT analysis set will be used for the analysis of efficacy endpoints [REDACTED]

[REDACTED] and will be presented by "as-assigned" infusion duration group. Summaries will be categorized based on the infusion duration assigned at Day 1 visit.

PK and ADA endpoints will be analyzed by "as assigned" infusion duration group for the PK analysis set. MTX polyglutamate analyses will be presented by "as assigned" infusion duration group using the mITT analysis set. Remaining primary, secondary, exploratory, and safety endpoints analyses will be summarized for the safety analysis set and will be presented by "as-assigned" treatment group.

[figure not shown]
Select safety analyses may also be summarized by "as-treated" group if at least 3 subjects in an assigned infusion duration group receive an infusion at a duration that differs from their assigned duration. Given the possibility of subjects switching from the assigned duration to other durations, subjects will fall into a specific treatment duration group (i.e. column header N) if they

have at least one infusion done at the indicated infusion duration. If a subject is treated with more than one infusion duration, then that subject will be counted in both infusion duration groups' denominator. Results corresponding to the infusion subjects actually take at any moment in the study will be windowed based on start date and time of each treatment and summarized in the corresponding treatment group category. One subject's results may appear in multiple treatment categories depending on what treatment was taken at each point in the study. Additional details on windowing for determination of actual treatment status for a specific result are described in Treatment Windowing (Section 3.1.5).

Data for the Pegloticase + MTX Period will be summarized descriptively by infusion duration regimen as described above, unless otherwise specified. In other words, analyses of the mITT or safety analysis sets in any period will be presented by infusion duration group: “60-Min Pegloticase + MTX”, “45-Min Pegloticase + MTX”, “30-Min Pegloticase + MTX”. If other infusion durations > 60 minutes are used in the study, then those will be presented in a separate treatment group: “> 60-Min Pegloticase + MTX” for any analyses done by “as treated” group.

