Prior to the Pegloticase + MTX Period, subjects will begin taking at least one of the per protocol standard gout flare prophylaxis regimen (colchicine 0.6 mg/day and/or nonsteroidal anti-inflammatory drug (NSAID) and/or low dose prednisone <10 mg/day) for  $\geq 1$  week before the first dose of pegloticase and continues flare prophylaxis throughout the pegloticase treatment period per American College of Rheumatology guidelines [FitzGerald JD et al. 2020].

For infusion reactions prophylaxis, fexofenadine (180 mg orally) will be taken the night before each infusion; fexofenadine (180 mg orally) and acetaminophen (1000 mg orally) will be taken the morning of each infusion; and methylprednisolone (125 mg IV) over an infusion duration between 10 and 30 minutes, will be administered immediately prior to each infusion.

During the Pegloticase + MTX Period, all subjects will receive pegloticase 8 mg every 2 weeks administered IV for a total of 12 infusions from Day 1 through Week 22, inclusive.

Up to three pegloticase infusion durations will be assessed in the Pegloticase + MTX Period: 60-minute infusion, 45-minute infusion and 30-minute infusion. Cohorts of approximately 10 subjects will be enrolled sequentially at progressively shorter infusion durations initially, beginning with the 60-minute infusion duration, progressing down to the 45-minute infusion duration and then to the 30-minute infusion duration. If deemed safe, enrollment will continue until approximately 110 subjects are enrolled (e.g. 110 subjects in the 30-minute infusion cohort, unless 30-minute infusion was not tolerated and then up to approximately 110 subjects may be enrolled in the 45-minute or 60-minute infusion cohort). The most desirable infusion duration is the shortest duration which is shown to be safe and well tolerated. Safety will be continuously monitored, and if any safety concerns are identified in any of the given enrollment infusion duration cohorts, screening/enrollment may be paused until safety data is evaluated by the Safety Review Committee (SRC) and/or restarted at the same or another infusion duration.

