Investigators will be permitted to adjust the duration of the infusion at a particular infusion visit regardless of initial treatment duration assignment, if needed. The decision to modify the

infusion duration at a visit will be allowed based on the investigator's discretion. Subjects may return to the original infusion duration for subsequent infusions.

Pegloticase will be administered after all pre-dose study visit assessments have been completed at each visit. The date and time of infusion start and stop will be recorded.

Samples for measurement of sUA levels, PK analysis of pegloticase, pegloticase immunogenicity and MTX Polyglutamate analysis will be collected at visits indicated in the Schedule of Events (Section 2.1 in the protocol).

Safety assessments, including monitoring and recording of all AEs, whether or not drug-related, measurement of vital signs, physical examinations and monitoring of hematology and blood chemistry, will be performed.

Adverse events of special interest (AESIs) defined in the protocol are gout, IRs, anaphylaxis and cardiovascular events. All AESIs except gout flare will be adjudicated by a team of external experts with experience in immunology, allergic reactions, rheumatology and/or cardiovascular diseases.

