### 1.1.3 Determination of Sample Size

Approximately 10 subjects will be enrolled sequentially at progressively shorter infusion durations, beginning with the 60-minute infusion duration, progressing down to the 45-minute infusion duration and then to the 30-minute infusion duration. Approximately 110 subjects are planned to be enrolled into a desirable infusion cohort that does not meet the dose limiting criteria. Therefore, the total number of subjects enrolling across the 3 different cohorts in the study is approximately 130.

Based on the MIRROR-RCT study, we expect approximately 5.0% of subjects to have an IR (including events of anaphylaxis) when taking pegloticase concurrently with MTX. The sample size of 110 for the selected cohort is chosen to ensure a high probability of ruling out an unacceptably high IR rate. If the observed IR rate is 5%, there is a greater than 80% probability that the upper bound of the two-sided 95% exact confidence interval for the IR rate is less than 13%.

[figure not shown]

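### As-treated tables count a subject in full at every infusion duration received, so infusion-reaction percentages depend on how many infusions each column holds

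*SAP*

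**What the plan says.** SAP 3.1.2 makes as-assigned the default presentation. Selected safety analyses may additionally be shown by duration actually received, the trigger being: "group if at least 3 subjects in an assigned infusion duration group receive an infusion at a duration that differs from their assigned duration". The analyses to be selected are not named, and SAP 3.6.1 again leaves as-treated analyses to be done only if warranted.

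For these tables SAP 3.1.2 gives two counting rules.

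- **Denominator.** One infusion is enough for entry to a column: the requirement is to "have at least one infusion done at the indicated infusion duration". Overlap between columns is explicit: when a "subject is treated with more than one infusion duration, then that subject will be counted in both infusion duration" columns.
- **Numerator.** Results are allocated to the duration in use at the time: "One subject's results may appear in multiple treatment categories depending on what treatment was taken at each point in the study".

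There is also a column for departures from assignment: "If other infusion durations > 60 minutes are used in the study, then those will be presented in a separate treatment group". Assigned durations are 60, 45 and 30 minutes, so only changes of duration can fill it. SAP 1.1.2 lets the investigator change the duration at a single visit and adds: "Subjects may return to the original infusion duration for subsequent infusions". The worked example in SAP 3.1.6 is a subject given a 120-minute infusion at Week 2.

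For the as-treated columns the SAP sets no minimum number of infusions, no weighting and no exposure base.

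**The concern.** The numerator covers only the part of a subject's treatment given at one duration. The denominator counts the whole subject. The resulting percentage therefore mixes risk per infusion with the number of infusions per subject in the column, and the table sets such columns side by side.

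Unequal exposure is to be expected, because a change may last for one visit only. A subject given eleven 30-minute infusions and one slower infusion counts as 1 in both columns.

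Two other planned summaries might be expected to correct this, but as written they do not.

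- The exposure-adjusted incidence rate in SAP 3.6.3.3 counts time from the Day 1 visit to the event or last dose. It is not split at changes of duration, and its table has no IR row.
- SAP 3.6.3.4 counts IR events per infusion, but does not tie that count to the duration received.

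At stake is how a reader would take a table that lays out IRs by duration. A briefly used, slower duration would look safer than the assigned one for a purely arithmetical reason.

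**Working it through.** **The plan's own IR figure.** SAP 1.1.3 gives a probability above 80% that the exact two-sided 95% upper bound is below 13%, with n = 110 and a 5% rate. The Clopper-Pearson upper bound is 12.67% for 7/110 and 13.83% for 8/110, so at most 7 subjects with an IR are allowed. P(X ≤ 7 | 110, 0.05) = 0.814, so the figure is reproduced. The documents give no figure for the as-treated tables.

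**Inputs from the documents**

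- Infusions per subject: 12 (SAP 1.1.2: "administered IV for a total of 12 infusions from Day 1 through Week 22, inclusive").
- Expected IR rate: 5.0% (SAP 1.1.3: "we expect approximately 5.0% of subjects to have an IR (including events of anaphylaxis) when taking pegloticase concurrently with MTX").
- Selected cohort: 110 subjects (SAP 1.1.3).

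**Assumptions added here.** The risk per infusion is constant and independent and the same at every duration. All 12 infusions are given. The numbers of switchers are illustrative.

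**Risk per infusion.** 1 − (1 − q)^12 = 0.05, so q = 1 − 0.95^(1/12) = 0.00427, or 0.43%.

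**Expected column percentage** when each subject in the column has k infusions at that duration: 1 − (1 − q)^k. The 12-infusion risk is varied to show the range. The value 13% is the SAP's criterion, and 26% is the Phase 3 IR rate in Protocol 7.1.2.

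| Risk over 12 infusions | k = 1 | k = 2 | k = 6 | k = 12 |
|---|---|---|---|---|
| 5% | 0.43% | 0.85% | 2.53% | 5.00% |
| 10% | 0.87% | 1.74% | 5.13% | 10.00% |
| 13% | 1.15% | 2.29% | 6.73% | 13.00% |
| 26% | 2.48% | 4.89% | 13.98% | 26.00% |

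**Example at 5%.** Of 110 subjects assigned 30 minutes, 20 have some infusions above 60 minutes.

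- One slow infusion each: the 30-minute column is (90 × 5.00% + 20 × 4.59%)/110 = 4.93% and the slow column is 0.43%, a ratio of 11.5. In 20,000 simulated trials the means were 4.93% and 0.42%.
- Two each: 4.85% against 0.85%, ratio 5.7.
- Six each: 4.55% against 2.53%, ratio 1.8.

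**What a single trial would show.** With one slow infusion per switcher, the probability of no IR in the slow column is (1 − q)^3 = 0.99 for 3 subjects (the minimum trigger) and (1 − q)^20 = 0.92 for 20.

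**Infusions as denominator.** With 20 subjects having one slow infusion each, there are 90 × 12 + 20 × 11 = 1,300 infusions at 30 minutes and 20 slow ones. The expected rate is 0.43 IRs per 100 infusions in both columns, so under equal risk the difference disappears.

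**The case against.** The strongest case on the other side has five parts.

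- **The tables are optional.** No text says that IRs will be among the selected analyses. The primary endpoint, with its 13% criterion in SAP 3.4.1, is presented as-assigned, and SAP 3.1.1 rules out inferential testing. All of this stands and limits the importance of the point.
- **Other planned output shows the duration received.** A reader might infer that the as-treated table is the only view by duration given. It is not: SAP 3.6.3.3 lists every adverse event with the duration corresponding to its onset, and SAP 3.3.1 plans shift tables from assigned to other durations. Neither gives a rate by duration received, so the gap remains.
- **Dilution of the 30-minute column.** A reader might infer that slowing subjects for good would pull the 30-minute percentage down materially. If 30 of 110 were slowed permanently after infusion 2, the column would fall to (80 × 5.00% + 30 × 0.85%)/110 = 3.87%. That needs 27% of subjects slowed for reasons other than an IR, which nothing in the documents supports. Protocol 9.5.7.2 and 9.5.7.3.2.4 link slowing to an IR, and a subject whose IR came at 30 minutes is already in that column's numerator.
- **An 11-fold contrast would seldom be seen.** It is a ratio of expectations. In practice the slow column would usually read 0/3 or 0/20, with N displayed. This also stands.
- **Constant risk is a simplification.** Protocol 7.1.2 and 7.2 relate IRs to antibodies and loss of urate response, so subjects slowed after an IR are likely to be at higher risk. A better denominator does not remove that confounding.

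None of this makes the two counting rules consistent. It limits the point to these tables, if they are produced for IRs.

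**Conclusion.** The point holds in a limited form. If as-treated tables are produced for IRs, SAP 3.1.2 yields percentages that are not comparable between durations, because a whole subject is divided into part of that subject's treatment. Under equal risk per infusion, the column with fewer infusions per subject shows the lower percentage: 0.43%, 2.5% and 5.0% for one, six and twelve infusions. These figures rest on constant, independent risk and on 5% over 12 infusions. The direction follows from the rule, while the size in this trial depends on a switching pattern that the documents do not give. Real columns would also carry selection after an IR, which may act in the other direction.

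A reader might infer that the trial's main conclusion is at risk. The documents do not support that: the primary objective concerns IR incidence in one chosen cohort, analysed as assigned. This is a worthwhile correction to a supplementary table.

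**What to change.** In SAP 3.1.2 and 3.1.6:

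1. State that any as-treated IR summary also reports infusions with an IR over the number of infusions given at each duration. This extends the per-infusion summary of SAP 3.6.3.4 to duration received. SAP 3.6.3.5 already uses infusion-level denominators.
2. Classify each infusion by the duration planned at its start. SAP 3.6.2 already summarises planned duration. SAP 3.1.6 uses the treatment actually given for post-infusion results, so an infusion slowed because of a reaction could otherwise be filed under the slower duration.
3. Give an interval that allows for repeated infusions per subject. For a column with no events, show the counts, because resampling and robust-variance intervals collapse there.
4. Keep the number of subjects ever exposed as a descriptive header.
5. For other adverse events shown as-treated, use person-time split at each change of duration.
6. Add a table note that the columns are non-randomised and confounded, because slowing often follows an IR, and are descriptive only.
7. Correct the cross-reference in SAP 3.1.2, which points to 3.1.5 for treatment windowing; the rules are in 3.1.6.

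The cost is SAP wording and some extra programming. Infusion start and stop times are already recorded (SAP 1.1.2), and the primary analysis does not change.

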### 3.1.3 Definition of Baseline

The MTX baseline is defined as the last non-missing observation prior to the first dose of MTX. The following assessments will utilize the MTX baseline when assessing changes from baseline or shift tables within the MTX Run-in Period and the Pegloticase + MTX Period:

- Vital signs

- Hematology and chemistry laboratory parameters

The pegloticase baseline is defined as the last non-missing observation prior to the first dose of pegloticase. The following assessments will use the pegloticase baseline when assessing changes from baseline or shift tables within the Pegloticase + MTX Period:

- Vital signs

- MTX polyglutamate
- Pegloticase PK
- Urine albumin: creatinine ratio
- Antibody
- Hematology and chemistry laboratory parameters

Change from baseline for a time period will be calculated as the value at the time point of interest minus the appropriate baseline value for that time period.

### 3.1.4 Study Day

Two different study days will be calculated. The first study day (MTX study day) will be determined relative to the first dose of MTX in the MTX Period. The second study day (Pegloticase study day) will be determined relative to the first infusion of pegloticase.

For both study day calculations, for study days on or after the first dose date the study day will be calculated as assessment date – first dose date + 1. For study days prior to the first dose date, study day will be calculated as assessment date – first dose date. Therefore, there will be no study day 0.

### 3.1.5 Visit Windowing

For all analyses, data will be summarized according to the scheduled visit and time points as outlined in the protocol and by the visit denoted on the electronic case report form (eCRF). The reference date associated with each visit is collected on the Visit Date eCRF page. Further, the End of Study/Early Termination (ET) visit and the End of Pegloticase Infusion Visit will be windowed to a visit based on the study day of occurrence relative to the target day of each scheduled visit according to Tables 1-8 below.

**Table 1: Visit Windows for Assigning End of Study/ET and End of Pegloticase Visits to a Scheduled Visit (Vital Signs, sUA)**

Study Period	Visit	Target Day a	Window for Reassignment to Scheduled Visit (days)
Pegloticase + MTX	Day 1	1	1
	Week 2	15	2 – 22
	Week 4	29	23 – 36
	Week 6	43	37 – 50
	Week 8	57	51 – 64
	Week 10	71	65 – 78
	Week 12	85	79 – 92
	Week 14	99	93 – 106
	Week 16	113	107 – 120
	Week 18	127	121 – 134
	Week 20	141	135 – 148
	Week 22	155	149 – 162
	Week 24	169	≥ 163

a Study days in the Pegloticase + MTX Period will be calculated relative to the first dose of Pegloticase.

**Table 2: Visit Windows for Assigning End of Study/ET and End of Pegloticase Visits to a Scheduled Visit (Laboratory Assessments and Urine Albumin: Creatinine Ratio)**

Study Period	Visit	Target Day a	Window for Reassignment to Scheduled Visit (days)
Pegloticase + MTX	Day 1	1	1
	Week 2	15	2 – 29
	Week 6	43	30 – 71
	Week 14	99	72 – 127
	Week 22	155	128 – 162
	Week 24	169	≥ 163

a Study days in the Pegloticase + MTX Period will be calculated relative to the first dose of Pegloticase.

[figure not shown]
**Table 3: Visit Windows for Assigning ET and End of Pegloticase Visits to a Scheduled Visit (Pegloticase PK and Antibody testing)**

Study Period	Visit	Target Day a	Window for Reassignment to Scheduled Visit (days)
Pegloticase + MTX	Day 1	1	1
	Week 2	15	2 – 29
	Week 6	43	30 – 64
	Week 12	85	65 – 113
	Week 20	141	114 – 155
	Week 24	169	≥ 156

a Study days in the Pegloticase + MTX Period will be calculated relative to the first dose of Pegloticase.

**Table 4: Visit Windows for Assigning ET and End of Pegloticase Visits to a Scheduled Visit (Pre-infusion MTX Polyglutamate PK)**

Study Period	Visit	Target Day a	Window for Reassignment to Scheduled Visit (days)
Pegloticase + MTX	Day 1	1	1
	Week 14	99	2 – 127
	Week 22	155	128 – 162
	Week 24	169	≥ 163

In the event that an End of Study/ET or End of Pegloticase visit is reassigned to a visit for which the subject has scheduled data collected, the data from the nominal scheduled visit will take precedence and the data from the End of Study/ET or End of Pegloticase visit will not be summarized. If the End of Study/ET or End of Pegloticase visit maps to a visit where the assessment was scheduled to be collected, and a scheduled collection is not available at that time point, the End of Study/ET or End of Pegloticase visit data will be summarized in the scheduled visit assessment.

